3.5	X	X	X					
4	X	X	X					X
6	X	X	X				X	
8	X	X	X					
12	X	X	X	X			X	
24	X	X	X	X	X	X	X	
48	X	X	X	X	X	X	X	
72	X	X	X	X	X	X	X	
96	X	X	X	X	X	X		
120	X	X	X	X	X	X		
144	X	X	X	X	X	X		
168	X	X	X	X	X	X		

^a Blood (4 mL blood to produce 2 mL plasma for assessment of selumetinib and metabolite).

^b Blood (4 mL for [¹⁴C] radioactivity determination is whole blood). Collection for radioactivity assessment may cease if less than 1% of the radioactive dose is detected in 2 consecutive plasma or urine samples.

^c Blood (4 mL to produce 2 mL for [¹⁴C] radioactivity determination in plasma). Collection for radioactivity assessment may cease if less than 1% of the radioactive dose is detected in 2 consecutive plasma samples.

^d Times indicated in the table present the stop-time of pooled collection. If emerging data indicates that adequate dose recovery has not been achieved after 7 days then some healthy volunteers may be asked to continue urine and/or faecal collections for a further 3 days either on an inpatient or an outpatient basis, and if adequate dose recovery is still not achieved, some healthy volunteers could be asked to return to the study centre approximately 7 days later, for a further 24 hour collection. Additional 24 hour collections of urine and/or faeces may continue until >90% mass balance cumulative recovery has been achieved or radioactivity counts are <1% on 2 consecutive samples (or recovery in urine/faeces in a 24 hour period is less than 1% of total administered dose of radioactivity on two consecutive collections).

^e Plasma (3 x 9 mL blood to produce plasma) for metabolite profiling and identification .

^f A portion of each sample will be sent to AstraZeneca Oncology iMed Alderley Park for metabolite identification, the remainder of the sample will be retained at for analysis of radioactivity.

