3.2 Rationale for study design, doses and control groups

Healthy male volunteers are considered appropriate because the PK data generated will not be influenced by any disease process or concomitant medication. It is expected that 6 healthy volunteers will be sufficient to provide a reliable estimate of rates and routes of excretion.

Selumetinib incorporating 22.57 MBq (610 µCi) of [¹⁴C] will be administered as a single dose of 75 mg (3 x 25 mg). This gives an effective dose (ED) of 4.52 mSv which falls within the radiolabeled category II dose, World Health Organisation 1977 and category IIb, International Commission on Radiological Protection 1992 guidelines.

The dose level of 75 mg is considered to be in the therapeutic dose range and is high enough to fully characterise the single oral dose PK of the parent compound and to enable metabolite quantification and identification, as part of a separate study. A dose of 75 mg twice daily is being investigated in ongoing efficacy studies of selumetinib. A radioactive dose of 22.57 MBq is considered to be the minimum dose of radioactivity that will be sufficient to achieve the study objectives.

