4.1 Inclusion criteria

For inclusion in the study healthy volunteers should fulfil the following criteria:

1. Provision of signed and dated, written informed consent prior to any study specific procedures.
2. Regular bowel movements (ie, on average production of at least 1 stool per day).
3. Healthy male volunteers aged 50 to 65 years (inclusive) with suitable veins for cannulation or repeated venipunctures. (Healthy as determined by medical history, physical examination, laboratory parameters, ECG, echocardiogram, and eye examination performed predose.)
4. Have a body mass index (BMI) between 18 and 32 kg/m² inclusive and weigh at least 50 kg and no more than 100 kg, inclusive.
5. Calculated creatinine clearance (CRCL) greater than 50 mL/min using Cockcroft-Gault formula.

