6.5 Patient reported outcomes (PRO) (Not applicable)

6.6 Pharmacokinetics

6.6.1 Collection of samples

Separate blood samples will be taken for the determination of total blood radioactivity, selumetinib (and N-desmethyl selumetinib), and [¹⁴C] radioactivity in plasma and for metabolic profiling.

Venous blood samples for the determination of concentrations of total radioactivity in whole blood (approximately 4 mL) and plasma (approximately 4 mL) will be taken at the times presented in the Study Plans (Table 2 and Table 3). The actual date and time of collection will be recorded in the appropriate sections of the CRF.

Venous blood samples for the determination of concentrations of selumetinib and N-desmethyl selumetinib (approximately 2 mL of whole blood) in plasma will be taken at the times presented in the Study Plans (Table 2 and Table 3). The actual date and time of collection will be recorded in the appropriate sections of the CRF.

Venous blood samples will be taken for use in an additional study in order to quantify and characterise metabolites in plasma. Approximately 3 x 9 mL of blood will be taken at the times presented in the Study Plans (Table 2 and Table 3). The actual date and time of collection will be recorded in the appropriate sections of the CRF.

Urine samples for determination of total radioactivity in urine will be taken at the time intervals presented in the Detailed Study Plan (Table 3). For the pooled urine collections, healthy volunteers will void all urine before dosing, and a predose urine sample will be retained for further metabolite identification studies. Following consumption of the radioactive dose, each healthy volunteer's urine will be collected as voided into screw top plastic containers, using separate containers for each collection period. The total urine volume of each urine collection will be recorded. The actual start and stop dates and times of the pooled collection will be recorded in the appropriate sections of the CRF. Samples collected must be kept refrigerated (approximately 4°C) during each collection period.

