11.3 Calculation or derivation of patient reported outcome variables (Not applicable)

11.4 Calculation or derivation of pharmacokinetic variables

The PK analyses of [¹⁴C] radioactivity concentration data in whole blood, plasma, urine, and faeces and selumetinib and N-desmethyl selumetinib concentration data in plasma will be performed at . Pharmacokinetic analyses will be conducted according to Standard Operating Procedures unless otherwise specified.

Total [¹⁴C] radioactivity in whole blood and plasma will be converted to concentration equivalents of selumetinib based on the actual specific activity of the dose.

Pharmacokinetic parameters will be determined using standard noncompartmental methods with WinNonlin[®] Professional Version 5.2 or higher

or SAS[®] Version 9.2 or higher

Actual elapsed time from dosing will be used for final blood-based

PK parameter calculations. Pharmacokinetic parameter units will be consistent with the concentration units specified in the bioanalytical data.

The following PK parameters will be determined for plasma selumetinib and N-desmethyl selumetinib and whole blood and plasma [¹⁴C] radioactivity:

AUC	Area under the concentration-time curve in the sampled matrix from time zero to infinity, calculated by linear up/log down trapezoidal summation
AUC _(0-t)	Area under the concentration-time curve in the sampled matrix from time zero to the time of the last quantifiable concentration, calculated by linear up/log down trapezoidal summation
AUC ₍₀₋₁₂₎	Area under the concentration-time curve in the sampled matrix from time zero to the time of 12 hours, calculated by linear up/log down trapezoidal summation
C _{max}	Maximum concentration in the sampled matrix, obtained directly from the observed concentration versus time data
t _{max}	Time to C _{max}
CL/F	Apparent oral plasma clearance (selumetinib only, whole blood and plasma radioactivity only)
V _{ss} /F	Apparent volume at distribution equilibrium, mean residence time (MRT)*CL/F (selumetinib only, whole blood and plasma radioactivity only)
V _z /F	Apparent volume at distribution (selumetinib only, whole blood and plasma radioactivity only)
t _{1/2}	Terminal half-life
λ _z	Terminal rate constant
MR _{AUC}	AUC metabolite to parent ratio, N-desmethyl selumetinib AUC/selumetinib AUC

$MR_{C_{max}}$	C_{max} metabolite to parent ratio, N-desmethyl selumetinib $C_{max}/\text{selumetinib } C_{max}$

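### The 1%-of-dose criterion for stopping blood radioactivity sampling is met by every plasma sample, so it cannot show that radioactivity is exhausted

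*Protocol*

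**What the plan says.** Table 3 (Protocol Section 3.1) schedules 19 plasma and 19 whole-blood radioactivity samples from 0 to 168 hours. Section 6.6.1 repeats that blood for radioactivity in "whole blood (approximately 4 mL) and plasma (approximately 4 mL) will be taken at the times presented in the Study Plans".

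Two footnotes allow earlier stopping. For plasma, footnote c reads: "Collection for radioactivity assessment may cease if less than 1% of the radioactive dose is detected in 2 consecutive plasma samples". For whole blood, footnote b reads: "Collection for radioactivity assessment may cease if less than 1% of the radioactive dose is detected in 2 consecutive plasma or urine samples". Footnote c also gives the sample size: 4 mL of blood yielding 2 mL of plasma. Neither footnote sets an earliest time, refers to the peak or to the LLOQ, or scales the sample to the volunteer's plasma volume.

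The dose is given in Section 3.2: selumetinib carrying 22.57 MBq "will be administered as a single dose of 75 mg (3 x 25 mg").

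Section 11.4 converts whole-blood and plasma radioactivity to concentration equivalents of selumetinib. It defines percent of dose only for urine, faeces and total recovery. The laboratory's running recovery calculation in Section 12.2.2.1 likewise covers urine and faeces only.

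**The concern.** A percent-of-dose threshold makes sense for a complete 24-hour urine or faecal collection, which is how footnote d uses it. A 2 mL plasma sample is a tiny fraction of the plasma pool, so a share-of-dose threshold for it may be out of reach at any time, peak included. A criterion that is always true cannot separate a measurable terminal phase from one that has ended, and stopping becomes a matter of discretion that may differ between volunteers.

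The two footnotes also differ. Whole blood may stop on urine results and plasma may not. Secondary objective 3 compares plasma with whole blood, and Section 11.4 requires the whole blood:plasma ratio and the percentage in blood cells at each sampling time. Both need paired samples.

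At stake are the late blood-based radioactivity data. Section 11.4 states: "The following PK parameters will be determined for plasma selumetinib and N-desmethyl selumetinib and whole blood and plasma" radioactivity. The parameters include half-life and AUC to infinity, and the synopsis lists the radioactivity parameters under its primary endpoints. A profile cut short has a larger extrapolated area, and Section 11.4 withholds AUC to infinity when more than 20% is extrapolated.

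**Working it through.** **Inputs from the Protocol**
- Dose: 75 mg and 22.57 MBq (610 µCi), Section 3.2.
- Plasma sample: 2 mL from 4 mL of blood, Table 3 footnote c. Section 6.6.1 agrees on about 4 mL of blood.
- Threshold: 1% of the radioactive dose, footnotes b and c.
- Body weight: "weigh at least 50 kg and no more than 100 kg, inclusive", Section 4.1.

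**Assumption:** the Protocol gives no plasma volume. I take 2.0 to 5.0 L to cover that weight range generously.

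**1. The Protocol's own dose figure.** 610 µCi × 0.037 MBq/µCi = 22.57 MBq, as stated. Three capsules of 7.52 MBq (Table 4) give 22.56 MBq, which agrees within rounding. The Protocol gives no derivation of the 1% plasma threshold, so there is nothing further to reproduce.

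**2. What 1% of the dose is.** 0.01 × 75 mg = 0.75 mg eq = 750 µg eq. In activity, 0.01 × 22.57 MBq = 225.7 kBq.

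**3. Concentration a 2 mL sample would need.** 750 µg ÷ 2 mL = 375 µg eq/mL. Equivalently, the whole dose would have to be confined to 2 mL ÷ 0.01 = 200 mL.

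**4. Upper bound on what a sample can hold.** Suppose 100% of the dose is in plasma at once, with nothing unabsorbed, in tissue or excreted. Share in the sample = sample volume ÷ plasma volume.

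| Assumed plasma volume | 2 mL sample | Times below 1% |
|---|---|---|
| 2.0 L | 0.10% | 10 |
| 3.0 L | 0.067% | 15 |
| 5.0 L | 0.04% | 25 |

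Counting the full 4 mL of blood as if it were plasma doubles these shares to 0.20% to 0.08%, still 5 to 12.5 times below the threshold.

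**5. Does meeting the criterion mean little is left?** No. At the 3.0 L bound a 2 mL sample would carry 22.57 × 10⁶ Bq × 60 × 2 ÷ 3,000 = 902,800 dpm and would still satisfy the criterion.

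**6. Footnotes side by side.** Whole blood: plasma or urine. Plasma: plasma only. Read literally, the plasma arm alone already permits both to stop. Once the plasma criterion is made meaningful, or if staff act on urine alone, the urine arm can end whole-blood sampling while plasma sampling continues.

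**The case against.** The strongest reply is that nothing compels stopping. Both footnotes are permissive, Table 3 and Section 6.6.1 make sampling to 168 hours the default, and Table 6 provides for all 19 samples of each kind. Counting results also arrive with delay. A reader might infer that the rule will end sampling at the first two time points. The documents do not support that: they permit it but do not direct it, and it is unlikely in practice. That the predose sample meets the criterion proves nothing either, since any threshold would be met then.

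A second reply is that the footnotes mean plasma concentration multiplied by total plasma volume. At an assumed 2.5 to 3.5 L this would put the threshold at 750 µg ÷ 2.5 L = 300 ng eq/mL down to 750 µg ÷ 3.5 L = 214 ng eq/mL, and it would not be met automatically near the peak. The text refers to what is detected in the samples, however, and no section defines such a calculation. A reader might go on to express that threshold as a multiple of the counting background. The Protocol gives no background or LLOQ for radioactivity, so no such multiple can be supported.

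A third reply concerns reach, and it stands. The 20% limit withholds AUC to infinity only; AUC(0-t), AUC(0-12) and Cmax carry no such limit. Parent and N-desmethyl sampling (footnote a) and metabolite-profiling sampling (footnote e) have no stopping clause. Urine and faecal recovery falls under footnote d, where percent of dose is meaningful. The study is descriptive, with no hypothesis test. It would be wrong to infer that the excretion result is compromised.

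**Conclusion.** The point holds as a defect in a stated rule. As written, the plasma criterion in footnotes b and c is always met: the most a 2 mL sample could hold is 10 to 25 times below 1% of the dose. Plasma volume is the only outside input, and the conclusion does not turn on it, since the criterion could fail only with the whole dose confined to 200 mL or less. It does rest on reading the footnotes literally, as the share of dose in the sample itself.

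The consequence is conditional. If staff use the option early, the late whole-blood and plasma radioactivity profiles are truncated. That affects half-life, AUC to infinity, the late whole blood:plasma ratios, and the late ratios of parent and metabolite to total radioactivity through their denominator. The documents do not allow the likelihood or size of such truncation to be estimated. The urine trigger is a separate, smaller inconsistency that can unpair the two matrices.

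This is not a matter for the SAP, which cannot restore samples that were never drawn.

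**What to change.** - Replace the percent-of-dose criterion in footnotes b and c with one concentration-based rule for paired whole-blood and plasma samples. For example: radioactivity sampling may stop only after quantifiable radioactivity has been observed and two consecutive post-peak plasma radioactivity concentrations are below the assay LLOQ. The post-peak condition is needed because the 0 h sample, and with slow absorption the 0.5 h sample, could both be below the LLOQ.
- Remove urine as a trigger for stopping whole blood.
- Keep percent-of-dose criteria for excreta only, as in footnote d.
- Reconcile the 168-hour blood schedule with the synopsis and Section 3.1. These let volunteers leave once cumulative recovery exceeds 90%, or once under 1% of the dose is collected over 2 consecutive days. Early discharge can end blood sampling whatever the footnotes say, so the Protocol should state how the two fit together.

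The cost is wording in two footnotes and a reconciling sentence. Table 6 already counts 19 samples of 4 mL for each matrix (76 mL + 76 mL), so no additional blood is needed.

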3.2 Rationale for study design, doses and control groups

Healthy male volunteers are considered appropriate because the PK data generated will not be influenced by any disease process or concomitant medication. It is expected that 6 healthy volunteers will be sufficient to provide a reliable estimate of rates and routes of excretion.

Selumetinib incorporating 22.57 MBq (610 µCi) of [¹⁴C] will be administered as a single dose of 75 mg (3 x 25 mg). This gives an effective dose (ED) of 4.52 mSv which falls within the radiolabeled category II dose, World Health Organisation 1977 and category IIb, International Commission on Radiological Protection 1992 guidelines.

The dose level of 75 mg is considered to be in the therapeutic dose range and is high enough to fully characterise the single oral dose PK of the parent compound and to enable metabolite quantification and identification, as part of a separate study. A dose of 75 mg twice daily is being investigated in ongoing efficacy studies of selumetinib. A radioactive dose of 22.57 MBq is considered to be the minimum dose of radioactivity that will be sufficient to achieve the study objectives.

4. SUBJECT SELECTION CRITERIA

Investigator(s) should keep a record, the healthy volunteer screening log, of healthy volunteers who entered prestudy screening.

Each healthy volunteer should meet all of the inclusion criteria and none of the exclusion criteria to be enrolled into this study. Under no circumstances can there be exceptions to this rule.

4.1 Inclusion criteria

For inclusion in the study healthy volunteers should fulfil the following criteria:

1. Provision of signed and dated, written informed consent prior to any study specific procedures.
2. Regular bowel movements (ie, on average production of at least 1 stool per day).
3. Healthy male volunteers aged 50 to 65 years (inclusive) with suitable veins for cannulation or repeated venipunctures. (Healthy as determined by medical history, physical examination, laboratory parameters, ECG, echocardiogram, and eye examination performed predose.)
4. Have a body mass index (BMI) between 18 and 32 kg/m² inclusive and weigh at least 50 kg and no more than 100 kg, inclusive.
5. Calculated creatinine clearance (CRCL) greater than 50 mL/min using Cockcroft-Gault formula.

4.2 Exclusion criteria

Volunteers should not enter the study if any of the following exclusion criteria are fulfilled:

1. Current or past history of central serous retinopathy or retinal vein thrombosis, intraocular pressure greater than 21 mmHg or uncontrolled glaucoma.
2. Radiation exposure from clinical studies, including that from the present study, excluding background radiation but including diagnostic X-rays and other medical exposures, exceeding 5 mSv in the last 12 months or 10 mSv in the last 5 years. No occupationally exposed worker, as defined in the Ionising Radiation Regulations 1999, shall participate in the study.
3. Left ventricular ejection fraction <55%.
4. Involvement in the planning and/or conduct of the study (applies to AstraZeneca, and staff).
5. History of any clinically important disease or disorder which, in the opinion of the Investigator, may either put the volunteer at risk because of participation in the study, or influence the results or the volunteer's ability to participate in the study.
6. History or presence of gastrointestinal, hepatic, or renal disease or any other condition known to interfere with absorption, distribution, metabolism, or excretion of drugs.
7. Any clinically important illness, medical/surgical procedure, or trauma within 4 weeks of the IP administration.
8. Any clinically important abnormalities in clinical chemistry, haematology, or urinalysis results as judged by the Investigator.
9. Any positive result on screening for serum hepatitis B surface antigen, hepatitis C antibody, and human immunodeficiency virus (HIV).
10. Any healthy volunteer with a clinically important abnormality in vital signs as assessed by the Investigator.
11. Any healthy volunteer with any clinically important abnormalities in their 12-lead ECG as assessed by the Investigator.
12. Known or suspected history of drug abuse as judged by the Investigator.
13. Current smokers or those who have smoked or used nicotine products within the previous 3 months.

14. History of alcohol abuse or current excessive intake of alcohol as judged by the Investigator.
15. Positive screen for drugs of abuse, cotinine (nicotine) or alcohol at screening or admission to the unit prior to the IP administration.
16. History of severe allergy/hypersensitivity or ongoing clinically important allergy/hypersensitivity, as judged by the Investigator or history of hypersensitivity to drugs with a similar chemical structure or class to selumetinib.
17. Excessive intake of caffeine containing drinks or food eg coffee, tea, chocolate, Red Bull, or cola (more than 6 units of caffeine per day). One caffeine unit is contained in the following items: 1 (6 oz) cup of coffee, 2 (12 oz) cans of cola, 1 (12 oz) cup of tea, ½ (4 oz) cup of energy drink (eg Red Bull), or 3 oz of chocolate.
18. Use of drugs with enzyme inducing properties such as St John's Wort within 4 weeks prior to the IP administration.
19. Use of any prescribed or non-prescribed medication including antacids, analgesics other than paracetamol/acetaminophen, herbal remedies, vitamins or excluding routine vitamins but including megadose (intake of 20 to 600 times the recommended daily dose) and minerals during the 3 weeks prior to the IP administration or longer if the medication has a long half-life. Exceptions may apply if considered not to interfere with the objectives of the study on a case by case basis if agreed by both the Principal Investigator and the Sponsor's medical monitor.
20. Any intake of grapefruit, grapefruit juice, Seville oranges, Seville orange marmalade, or other products containing grapefruit or Seville oranges within 7 days prior to admission on Day -1.
21. Plasma donation within 1 month of screening or any blood donation/blood loss 500 mL during the 3 months prior to screening.
22. Has received another new chemical entity (defined as a compound which has not been approved for marketing) or has participated in any other clinical study that included drug treatment within at least 3 months of the administration of IP in this study. The period of exclusion starts 3 months after the final dose or 1 month after the last visit whichever is the longest. Note: volunteers consented and screened, but not randomised in this study or a previous phase I study, are not excluded.
23. Judgment by the Investigator that the volunteers should not participate in the study if they have any ongoing or recent (ie, during the screening period) minor medical complaints that may interfere with the interpretation of study data or are considered unlikely to comply with study procedures, restrictions, and requirements.

24. Volunteers who have previously received selumetinib.
25. Volunteers who are vegans or have medical dietary restrictions.
26. Volunteers who cannot communicate reliably with the Investigator.

Any clinically important abnormalities in clinical chemistry, haematology, or urinalysis results as judged by the Investigator.

Procedures for withdrawal of incorrectly enrolled volunteers see Section 5.3.

